2.3.1 Does this research study involve a placebo-controlled arm?

* No

[\[reviewer notes-\]](#)

2.4 Will any research subjects be withdrawn from known effective therapy for the purpose of participating in this research study?

* No

[\[reviewer notes-\]](#)

2.5 Will screening procedures (i.e., procedures to determine research subject eligibility) be performed specifically for the purpose of this research study?

* Yes

2.5.1 List the **screening procedures that will be performed for the purpose of this research study. Do NOT include the inclusion/exclusion criteria in this section as they will be addressed in section 3; questions 3.13 and 3.14.**

To determine eligibility, potential participants will complete a brief online screening questionnaire before being entered into this study.

[\[reviewer notes-\]](#)

2.6

Provide a detailed description of all research activities (e.g., all drugs or devices; psychosocial interventions or measures) that will be performed for the purpose of this research study.

This description of activities should be complete and of sufficient detail to permit an assessment of associated risks.

At a minimum the description should include:

- **all research activities**
- **personnel (by role) performing the procedures**
- **location of procedures**
- **duration of procedures**
- **timeline of study procedures**

DESCRIPTION OF PARTICIPANT FLOW

1. Advertisements direct potential participants to Screener survey
2. Participants complete screener (in REDCap)
3. If eligible, participants complete informed assent/consent (in REDCap)
 - o If ineligible, participants are thanked for their time and no more contact is made with them.
4. If consent is provided, participants are emailed/texted a link to the baseline survey (T1) to complete (in REDCap)
 - o Incentive: \$10 when T1 survey is completed
5. Researchers then randomize participants to intervention or control (in REDCap)
6. All participants (both intervention and control groups) receive a list of website resources related to study outcomes. [This document is located in the 'Supporting Documentation Section' of this IRB Protocol.]
7. Intervention group receives Intervention Download Instructions (via Redcap) [This document is located in the 'Supporting Documentation Section' of this IRB Protocol. IRB Reviewers can use this document to download the game.]

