Does this research study involve the long-term storage (banking) of biological specimens?

* No

[\[reviewer notes-\]](#)**2.16**

Will research participants be asked to provide information about their family members or acquaintances?

* No

[\[reviewer notes-\]](#)**2.17**

What are the main outcome variables that will be evaluated in this study?

The primary outcomes of this study are related to feasibility. This includes the domains of acceptability, demand, implementation, practicality, integration, adaptation, expansion, and preliminary efficacy testing (based on Bowen, et al., 2009, Am J Prev Med). Below, we present each of the feasibility domains, how they will be measured, and corresponding hypotheses (in parentheses).

ACCEPTABILITY

- Measured using the Gaming Experience Questionnaire (average ≥ 2 in each domain)
- Would you recommend that your friends play this game? ($\geq 75\%$)
- How likely would you be to tell your friends about this game? ($\geq 80\%$)

DEMAND

- The number of hours the game was played ($\geq 75\%$ who played for ≥ 1 hour)
- Intervention group's self-reported use of the game in hours ($\geq 75\%$ who played for ≥ 1 hour)

IMPLEMENTATION

- How many participants in in the intervention arm downloaded the game? ($\geq 80\%$)
- How many people played the game? ($\geq 80\%$)
- How many people completed surveys at T1, T2, T3? ($\geq 80\%$ each survey wave)

- How many people completed ALL surveys? ($\geq 75\%$)
- How many people completed at least 2 surveys? ($\geq 85\%$)
- How many reminders before people completed the surveys? (exploratory)
- How well they did in the game? Did they meet the milestones in the game? (exploratory)
- How many times texted before they completed survey? (exploratory)
- How many times contacted? (exploratory)
- Percent of people who consented post screening (80%)
- How long does it take to get 240 people to enroll in the study? (exploratory)
- Did randomization work? (yes, we hypothesize no group differences in demographics at baseline)
- How many got randomized? (240 participants)
- How many people recruited from which venue? (exploratory)

PRACTICALITY

- How many people have PC or Mac computers in our screening procedures (exploratory)
- Screening based on having an email address (exploratory)
- How easily was the game downloaded without contacting our research coordinator? (exploratory)
- Feelings of safety with regards to password protection? (exploratory)

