- Feelings of safety with regards to having other people see the game? (exploratory)
- Did the game interfere with other activities? (exploratory)

INTEGRATION

- How could this better fit into the youth's life? (exploratory)
- How well does this fit into youth's life now? (exploratory)
- How could the game be improved? (exploratory)

ADAPTATION

- Would you want to be able to play this game on your phone (an app)? (exploratory)
- Did you like this game on the computer? (exploratory)
- This game may not be appropriate for older kids. (how much do they agree with this? Exploratory)
- We will examine the Gaming Experience Questionnaire scores by gender, sexual orientation, race/ethnicity, age (exploratory)

EXPANSION

- How could the game be improved? (exploratory)
- What would you like to be added to the game? (exploratory)
- What would you like removed from the game? (exploratory)

PRELIMINARY EFFICACY TESTING

We hypothesize that the intervention group (versus control group) will have greater levels of change over time in the following outcomes:

1. Increased help-seeking self-efficacy, intentions, and behaviors
2. Increased coping strategies and coping flexibility
3. Increased knowledge and use of online resources
4. Decreased bullying and cyberbullying victimization
5. Decreased loneliness
6. Decreased mental health problems (anxiety, depression, suicidality)
7. Decreased substance use (alcohol, tobacco, and other drugs)
8. Decreased internalized sexual and gender minority stigma

2.18 Describe the statistical approaches that will be used to analyze the study data.

* Addressed below:

For the measures of acceptability, demand, implementation, practicality, integration, adaptation, and expansion, we will report results using descriptive statistics (i.e., percentages and frequencies for categorical variables, or means and standard deviations for continuous variables).

For the preliminary efficacy testing outcomes, we will use repeated measures (i.e., multilevel) statistical models using logistic or linear regression, depending on the distribution

of the outcomes. To examine whether there were greater improvements over time in the intervention group versus control group, we will test the interaction term of time by group. While we are powered to find medium effects (based on Cohen), our primary interest is in estimating the effect size and confidence interval width, which will help us power a future, larger randomized controlled trial.

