3.8 Does this research study involve neonates of uncertain viability or nonviable neonates?

* No

[\[reviewer notes-\]](#)

3.9 Fetal Tissues: Does this research involve the use of fetal tissues or organs?

* No

[\[reviewer notes-\]](#)

--->

3.10

What is the total number of subjects to be studied at this site, including subjects to be screened for eligibility?

Note: The number below is calculated by summing the data entered in question 3.11. Any additions or changes to the values entered in 3.11 will be reflected in 3.10.

* 480

3.11

Identify each of the disease or condition specific subgroups (include healthy volunteers, if applicable) that will be studied.

Click on the "Add" button and specify for each subgroup:

1) how many subjects will undergo research related procedures at this site; and

2) if applicable, how many subjects will be required to undergo screening procedures (e.g., blood work, EKG, x-rays, etc.) to establish eligibility. Do Not include subjects who will undergo preliminary telephone screening.

*

Subgroup	Number to undergo research procedures	Number to undergo screening procedures
View Control	120	240
View Intervention	120	240

3.12

Provide a statistical justification for the total number of subjects to be enrolled into this research study at the multicenter sites or this site.

* Described below:

This is a feasibility study, which is primarily being conducted to inform a larger randomized controlled trial. For a majority of our outcomes, we are reporting simple descriptive statistics (e.g., how long the game was played by participants). For preliminary efficacy testing, we are primarily interested in effect size and confidence interval estimation; we are NOT necessarily interested in finding statistically significant effects (see Bowen, 2009, Am J Prev Med). Nevertheless, we are powered to find medium effect sizes (based on Cohen, 1988).

[\[reviewer notes-\]](#)**3.13 Inclusion Criteria: List the specific criteria for inclusion of potential subjects.**

- Aged 14 to 18 years old
- English literate
- Lives in the United States
- Identifies as Sexual or Gender Minority
- Has a PC or Mac that is able to download games
- Has an email address
- Has been bullied or cyberbullied in the past 12 months

3.14 Exclusion Criteria: List the specific criteria for exclusion of potential subjects from participation.

- Not bullied or cyberbullied in the past 12 months

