*** Upload Data Security Form:**

Name

Modified Date

[R21 Data Security Assessment Form - v2.docx](#) 11/30/2017 2:18 PM**Address what precautions will be used to maintain the confidentiality of the research data collected in paper format if applicable:**

N/A

5.15.1**Does your research study require a data security review? Answer Yes if any of the following conditions are met:**

- Identifiable or *coded data will be collected, stored, or transmitted using any of the following technologies: mobile app, web-based site or survey, wearable device, text messaging, electronic audio, photographic, or video recording or conferencing **and/or**
- The IRB requested a data security review during their review of the study

* Yes

***Coded:** Identifying information (such as name) that would enable the investigator to readily ascertain the identity of the individual to whom the private information or specimens pertain has been replaced with a code (number, letter, symbol, or any combination) and a key to decipher the code exists, enabling linkage of the identifying information to the private information or specimens

5.16**If the subject withdraws from the study, describe what, if anything, will happen to the subject's research data or biological specimens.**

If the subject withdraws from the study, we will delete all the subject's data from our databases.

5.17**Following the required data retention period, describe the procedures utilized to protect subject confidentiality.** (e.g., destruction of research records; removal of identifiers; destruction of linkage code information; secured long-term retention)

Data will be devoid of all subject identifiers and stored in secure password-protected Pitt BOX drive. De-identified data will be retained indefinitely.

[\[reviewer notes-\]](#)**6.1**

Will research subjects or their insurance providers be charged for any of the procedures (e.g., screening procedures, research procedures, follow-up procedures) performed for the purpose of this research study?

*

No

[\[reviewer notes-\]](#)**6.2 Will subjects be compensated in any way for their participation in this research study?**

* Yes

6.2.1

Describe the amount of payment or other remuneration offered for complete participation in this research study.

Participants will be paid \$10 for completing baseline (Time 1) survey, \$25 for Time 2 survey, and \$50 for Time 3 survey.

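### For continuous outcomes, fitting one T1 mean for both arms would give confidence intervals as narrow or narrower from the same data; section 2.18 does not use the fact that T1 precedes randomisation

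*Combined protocol and SAP*

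**What the plan says.** Section 2.18, repeated under Statistical Analysis in the opening study design part, plans multilevel linear or logistic models for the preliminary efficacy outcomes and states that "we will test the interaction term of time by group". It does not say whether the arms have separate or common T1 means, whether T1 is adjusted for, how time is coded, or which covariance structure is used. The hypothesis in section 2.17 is that the intervention group "will have greater levels of change over time in the following outcomes".

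The stated goal is precision of estimation. Section 2.18 says "our primary interest is in estimating the effect size and confidence interval width", to help power a larger trial. Section 3.12 repeats that "we are primarily interested in effect size and confidence interval estimation" and puts statistical significance second.

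In the participant flow of section 2.6, the T1 survey is step 4 and randomisation is step 5. Section 5.16 adds a rule that bears on the analysis: "If the subject withdraws from the study, we will delete all the subject's data from our databases".

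**The concern.** The usual model with group, time and group-by-time terms estimates a T1 mean for each arm. The interaction is then a difference in change, and each arm's T1 sampling error enters the contrast. Because T1 is measured before allocation, any T1 difference between the arms as randomised is chance, and estimating it costs precision.

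With one common T1 mean μ₁, the group difference at T2 is the difference in change:

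(μ_I,T2 − μ₁) − (μ_C,T2 − μ₁) = μ_I,T2 − μ_C,T2,

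and likewise at T3. So the hypothesis is unchanged. What is at stake is the width of the intervals that the plan names as its main efficacy product. The point does not depend on power or significance.

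**Working it through.** **Plan's own figure.** There is none to reproduce. The documents give no SD, within-person correlation or planned CI width.

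**Inputs from the documents.** 120 per arm (3.11). Targets of at least 80% at each wave, 75% completing all surveys and 85% completing at least two (2.17, Implementation).

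**Assumptions.** Every randomised participant has a T1 value, because T1 precedes randomisation. Retention pattern: 75% T1+T2+T3, 5% T1+T2, 5% T1+T3, 15% T1 only. This meets the targets: 75 + 5 = 80% at each of T2 and T3, and 75 + 5 + 5 = 85% with at least two. T1 SD = 1. The correlation ρ and the ratio s = follow-up SD / T1 SD are varied.

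**Formula, two waves.** With n at T1 and m at follow-up per arm, the variance contribution per arm is:

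- separate T1 means: s²(1 − ρ²)/m + (1 − ρs)²/n
- common T1 mean: s²(1 − ρ²)/m

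The difference is (1 − ρs)²/n, which is never negative and is zero only where ρs = 1.

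**Example.** ρ = 0.5, s = 1, n = 120, m = 0.80 × 120 = 96:

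- separate: 0.75/96 + 0.25/120 = 0.007813 + 0.002083 = 0.009896; SE = √(2 × 0.009896) = 0.1407; half-width 1.96 × SE = 0.276
- common: 0.75/96 = 0.007813; SE = √(2 × 0.007813) = 0.1250; half-width 0.245
- narrowing: 1 − 0.1250/0.1407 = 11.1%

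**Three-wave GLS.** Retention pattern above, compound symmetry, s = 1, contrast at T2 (same at T3). Half-widths come from unrounded SEs.

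| ρ | SE separate | SE common | Half-width separate | Half-width common | Narrower by |
|---|---|---|---|---|---|
| 0.3 | 0.1645 | 0.1375 | 0.322 | 0.269 | 16.4% |
| 0.5 | 0.1403 | 0.1246 | 0.275 | 0.244 | 11.2% |
| 0.7 | 0.1096 | 0.1026 | 0.215 | 0.201 | 6.4% |
| 0.9 | 0.0638 | 0.0625 | 0.125 | 0.122 | 2.1% |

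At ρ = 0.5 the variance ratio is (0.1403/0.1246)² = 1.27, which is worth about 27% more participants.

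**Other scenarios, percentage narrower:**

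| Scenario | ρ 0.3 | 0.5 | 0.7 | 0.8 | 0.9 |
|---|---|---|---|---|---|
| AR(1), s = 1, T3 contrast | 22.6 | 18.0 | 11.6 | 7.9 | 4.1 |
| Compound symmetry, s = 1.25 | 9.5 | 4.5 | 0.8 | 0.0 | 2.1 |
| Compound symmetry, s = 1.5 | 5.4 | 1.5 | 0.1 | 1.9 | 9.9 |

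A ratio above 1 is possible for bullying, because eligibility requires it in the past 12 months (3.13). The two tables span 0% to 23%. That span is not a bound: at s = 0.8, compound symmetry gives 21.0% at ρ = 0.5 and 27.8% at ρ = 0.2.

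**Finite samples.** 1000 simulated trials per case used 120 per arm, the same dropout, a true effect of −0.3 SD and an unstructured covariance estimated by maximum likelihood. At ρ 0.3, 0.5, 0.7 and 0.9 the mean SE was 16.8%, 11.6%, 6.6% and 2.3% smaller. Mean estimates from the common-mean model were −0.295 to −0.302. Coverage of the 95% CI was 94% to 96% for both models.

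**Effect of deletion under 5.16.** Suppose a share w = 5% of one arm is deleted and its T1 mean is d = 0.5 SD above the rest of that arm. The retained T1 mean shifts by −wd = −0.025.

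- Deletion depends on T1 alone: follow-up shifts by −0.025ρ. The separate-means contrast is biased by 0.025(1 − ρ), which is 0.018, 0.013, 0.008 and 0.003 SD at ρ 0.3, 0.5, 0.7 and 0.9. The common-mean model is biased by 0.
- Deletion depends on a stable trait: all waves shift by −0.025. The separate-means contrast is biased by 0. The common-mean model is biased by the same amounts in absolute size.

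At 10% deleted these figures double.

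**The case against.** The strongest reply is that the planned contrast is valid, the trial is a pilot with feasibility as its primary outcome, and no pilot conclusion is shown to change. That stands: this is a recommendation about efficiency, and nothing here invalidates the plan.

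Second, the text does not commit to separate T1 means, so the gain may already be built in. That also stands, and the claim is conditional on it.

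Third, the size is assumed throughout. The 22.6% case is AR(1) at ρ = 0.3, which implies a T1–T3 correlation of 0.3² = 0.09. At correlations of 0.7 to 0.9 with equal SDs the gain is 6.4% or less. The number of outcomes that will be modelled as continuous cannot be told from the documents.

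Fourth, the change is not wholly without cost. Randomisation guarantees equal expected T1 means for everyone randomised, but not among records left after arm-related deletion under 5.16, and the common-mean model is the more exposed one if withdrawal follows a stable trait. The bias in that example is small against half-widths of 0.12 to 0.32, and the separate-means contrast has its own exposure when withdrawal follows T1. This is a reason to report both models, not to forgo the narrower interval.

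**Conclusion.** The point holds as an efficiency gain for continuous outcomes. If 2.18 means separate T1 means per arm, one common T1 mean with an unstructured covariance estimates the same difference in change and, in large samples, is never less precise. The best single illustration is 11% narrower at ρ = 0.5 with equal SDs and the plan's target retention. The correlation, SDs and covariance structure behind that figure are assumptions. The gain vanishes where the correlation times the SD ratio equals 1, and is little or nothing if a common T1 mean or T1 adjustment was already intended. No gain is claimed for the multilevel logistic models.

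**What to change.** In section 2.18, and in the matching text of the study design part, specify for continuous outcomes:

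- time as categorical (T1, T2, T3), with T1 kept in the response vector
- one common T1 mean: no group term at T1, only group-by-T2 and group-by-T3 terms
- an unstructured covariance
- group differences at T2 and T3 with 95% CIs
- the contrast with separate T1 means as a sensitivity analysis, alongside the number withdrawn and deleted in each arm

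The narrowing comes from the common T1 mean; the other model items make the analysis definite. For binary outcomes the same constraint is an option the team may consider. If a common T1 mean or T1 adjustment was already intended, the only step is to say so.

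The cost is SAP wording and model code, with no new participants or surveys. One practical step is needed: a count of withdrawals by arm must be kept before the records are deleted. Section 5.13 already has withdrawals reviewed, but does not say by arm.

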3.1 What is the age range of the subject population?

14-18

3.2 What is their gender?

* Both males and females

Provide a justification if single gender selected:

3.3 Will any racial or ethnic subgroups be explicitly excluded from participation?

* No

If **Yes**, identify subgroups and provide a justification:

3.4 For studies conducted in the U.S., do you expect that all subjects will be able to comprehend English?

* Yes

[\[reviewer notes-\]](#)

3.5 Participation of Children: Will children less than 18 years of age be studied?

* Yes

3.5.1 Specify the age range of the children to be studied.

(Check all that apply below:)

*

Choices

14-17 years of age

3.5.2 Provide a rationale for the specific age ranges of the children to be studied:

This is an intervention designed specifically for young sexual and gender minority (SGM) youth. All game development procedures have been conducted in consult with SGM aged 14-17 and experts in the field of SGM youth.

Please see the background section of this IRB protocol. Generally, SGM youth are at far higher risk to be bullied by peers. There is very little systematic support available for these youth to help them cope with such bullying. Our program will focus on this age range to decrease negative outcomes associated with bullying victimization among this population.

3.5.3 Describe the expertise of the study team for conducting research with children within this age range:

Drs. [name] and [name] have studied SGM youth for the past 10 years including the assessment of sexual orientation, gender identity, bullying victimization, protecting SGM youth in schools, and longitudinal assessment of SGM populations. They have led qualitative and quantitative studies of SGM youth including the assessment of sexual

orientation, gender identity, bullying, mental health, substance use, HIV risks among SGM youth.

3.5.3.1

Have you obtained the following clearances from all research staff who may have direct contact with children under the age of 18? Direct contact under the law includes face-to-face, and telephonic or electronic, contact with minors. Please see the [Child Clearances](#) guidance document for further explanation?

Pennsylvania Department of Public Welfare Child Abuse History Clearance; Pennsylvania State Police Criminal Record Check; and FBI Criminal Background Check

Yes

Note: If No, once all clearances are obtained, a modification must be submitted.

If you selected N/A, please explain:

It is important to note that "direct contact" refers not only to face-to-face meetings but also extends to communication via phone (including text messaging), social media or internet. Direct contact also includes the care, guidance, supervision or control, or routine interaction with, minors. Conversely, a participating investigator or support staff member who does not have direct contact, either electronically or in person, with children does not need to obtain clearances (e.g., statistician, non-clinical laboratory personnel, etc.). If your research study provides babysitting services, the babysitters must have the required child clearances.

*** Note:** It is the **responsibility of the principal investigator** to ensure that all research staff have these clearances prior to any interaction with children. Contact Human Resources at [contact] for assistance with this process.

3.5.4

Describe the adequacy of the research facilities to accommodate children within this age range:*

Not applicable; research will be conducted in the child's normal environment.

Note: Experts and non-experts alike consider the use of computers and games to be a part of the normal environment for children. Various studies have implemented game-based intervention studies in this environment.

3.5.5

Permitted Categories of Research: The Federal Policy and FDA regulations governing human subject protections specify that research involving children must fall into one of the following permitted categories.

*

The research does not involve greater than minimal risk [45 CFR 46.404/21 CFR 50.51].

